9.3.12 General Safety Measures

As specified in each visit procedure, adverse events (AEs) (both elicited and observed) will be monitored throughout the study. All AEs (both elicited and observed) will be

promptly reviewed by the investigator for accuracy and completeness. All AEs will be documented on the appropriate eCRF.

If a female has a positive pregnancy test during the study, then the investigator will notify Ora immediately. The investigator shall request from the subject and/or the subject's physician copies of all related medical reports during the pregnancy and shall document the outcome of the pregnancy. The investigator will retain these reports together with the subject's source documents and will provide a copy of all documentation to Ora.

9.4 Schedule of Visits, Measurements and Dosing

9.4.1 Scheduled Visits

Refer to Appendix 1 for a schedule of visits and measurements.

9.4.2 Unscheduled Visits

These visits may be performed in order to ensure subject safety. All procedures performed at an unscheduled visit will be recorded in the source documents and on the Unscheduled Visit eCRF pages. Any procedure indicated in the eCRF that is not performed should be indicated as "Not done."

Evaluations that may be conducted at an Unscheduled Visit include:

- Slit-lamp Biomicroscopy
- Visual Acuity
- Intraocular Pressure
- Urine Pregnancy Test
- Dilated Fundoscopy
- Assessment of Adverse Events
- Assessment of concomitant medications and/or treatments
- Any other assessments needed in the judgment of the investigator.

9.5 Compliance with Protocol

Subjects will be instructed on proper instillation and storage of study drug at the end of Visits 1 through 8 and given written instructions. The subject's used and unused study drug ampules will be collected at each visit from Visit 2 up to and including Visit 9 to assess dosing compliance. Dosing compliance will be based on the unused ampule count.

These guidelines will be used by the Investigator for determining the subject's necessary compliance for the study and for recording deviations from this compliance.

9.6 Subject Disposition

9.6.1 Completed Subjects

A completed subject is one who has not been discontinued from the study.

9.6.2 Discontinued Subjects

Subjects may be discontinued prior to their completion of the study due to:

- subject request/withdrawal
- AEs
- protocol violations
- administrative reasons (e.g., inability to continue, lost to follow up)
- Sponsor termination of study
- other

Note: In addition, any subject may be discontinued for any sound medical reason.

Notification of a subject discontinuation and the reason for discontinuation will be made to Ora and/or Sponsor and will be clearly documented on the eCRF.

9.7 Study Termination

The study may be stopped at any time by the investigator, the Sponsor, and/or Ora with appropriate notification.

9.8 Study Duration

An individual subject's participation will involve nine visits over approximately a 14-week (~98 days) period (84 days of treatment and 14 days pre-screening).

9.9 Monitoring and Quality Assurance

During the course of the study an Ora monitor, or designee, will make routine site visits to review protocol compliance, assess IP accountability, and ensure the study is being conducted according to the pertinent regulatory requirements. The review of the subjects' medical records will be performed in a manner that adequately maintains subject confidentiality. Further details of the study monitoring will be outlined in a monitoring plan.

Regulatory authorities of domestic and foreign agencies, Ora quality assurance and or its designees may carry out on-site inspections and/or audits which may include source data checks. Therefore, direct access to the original source data will be required for inspections and/or audits. All inspections and audits will be carried out giving consideration to data protection as well as subject confidentiality to the extent that local, state, and federal laws apply.

10 ADVERSE EVENTS

10.1 Adverse Event

An AE is defined as any untoward medical occurrence associated with the use of an IP in humans, whether or not considered IP-related. An AE can be any unfavorable and unintended sign (e.g., an abnormal laboratory finding), symptom, or disease temporally associated with the use of an IP, without any judgment about causality. An AE can arise from any use of the IP (e.g., off-label use, use in combination with another drug or medical device) and from any route of administration, formulation, or dose, including an overdose. An AE can arise from any delivery, implantation, or use of a medical device, including medical device failure, subject characteristics that may impact medical device performance (e.g., anatomical limitations), and therapeutic parameters (e.g., energy applied, sizing, dose release, and anatomic fit) associated with medical device use.

All AEs spontaneously reported by the subject and/or in response to an open question from study personnel or revealed by observation, physical examination or other diagnostic procedures will be recorded in the source document and on the appropriate pages of the CRF. Any clinically relevant deterioration in clinical finding is considered an AE and must be recorded. When possible, signs and symptoms indicating a common underlying pathology should be noted as one comprehensive event.

Documentation regarding the AE should be made as to the nature, date of onset, end date, severity, relationship to IP, action(s) taken, seriousness, and outcome of any sign or symptom observed by the physician or reported by the subject upon indirect questioning. Exacerbation of conditions related to the signs and symptoms of Dry Eye will not be reported as an AE.

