10.1.2 Relationship to Investigational Product

The Investigator must assess whether they consider an AE to be drug-related. In assessing this relationship, the Investigator must use information about the conditions/concurrent medication, and chronology of the event relative to drug administration. The following definitions will be used:

- ***Definitely Related***
- ***Probably Related***
- ***Possibly Related***
- ***Unlikely to be related***
- ***Not Related***

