10.2 Serious Adverse Events

An AE is considered serious if, in the view of either the investigator or Sponsor, it results in any of the following outcomes:

- Death;
- A life-threatening AE;

Note: An AE is considered "life-threatening" if, in the view of either the investigator or Sponsor, its occurrence places the subject at immediate risk of death. It does not include an AE that, had it occurred in a more severe form, might have caused death.

- Inpatient hospitalization or prolongation of existing hospitalization;

Note: The term "inpatient hospitalization" refers to any inpatient admission (even if less than 24 hours). For chronic or long-term inpatients, inpatient admission includes transfer within the hospital to an acute/intensive care inpatient unit. Inpatient hospitalization does not include: emergency room visits; outpatient/same-day/ambulatory procedures; observation/short stay units; rehabilitation facilities; hospice facilities; nursing homes; or clinical research/phase 1 units.

Note: The term “prolongation of existing hospitalization” refers to any extension of an inpatient hospitalization beyond the stay anticipated or required for the reason for the initial admission as determined by the investigator or treating physician.

- A persistent or significant incapacity or substantial disruption of the ability to conduct normal life functions;

Note: A serious adverse event (SAE) specifically related to visual threat would be interpreted as any potential impairment or damage to the subject’s eyes (e.g., hemorrhage, retinal detachment, central corneal ulcer or damage to the optic nerve).

- A congenital anomaly/birth defect.
- Important medical events that may not result in death, are life-threatening, or require hospitalization may be considered serious when, based upon appropriate medical judgment, they may jeopardize the subject and may require medical or surgical intervention to prevent one of the outcomes listed in this definition.

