10.3.1 Reporting a Suspected Unexpected Adverse Reaction

All AEs that are ‘suspected’ and ‘unexpected’ are to be reported to Ora, the Sponsor and the IRB/IEC as required by the IRB/IEC, federal, state, or local regulations and governing health authorities.

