10.3.2 Reporting a Serious Adverse Event

To ensure subject safety, all SAEs, regardless of relationship to the IP, must be immediately reported. All information relevant to the SAE must be recorded on the appropriate CRFs. The investigator is obligated to pursue and obtain information requested by Ora and/or the Sponsor in addition to that information reported on the CRF. All subjects experiencing a SAE must be followed up and the outcome reported.

In the event of a SAE, the investigator must notify Ora and the Sponsor immediately; obtain and maintain in his/her files all pertinent medical records, information, and medical judgments from colleagues who assisted in the treatment and follow-up of the subject; provide Ora and the Sponsor with a complete case history, which includes a statement as to whether the event was or was not suspected to be related to the use of the IP; and inform the IRB/IEC of the SAE within their guidelines for reporting SAEs.

Contact information for reporting SAEs:

[REDACTED]	[REDACTED]

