11.4.9 Safety Variables

Adverse events will be coded using the MedDRA dictionary.

Frequencies and percentages will be provided per treatment group of subjects with treatment-emergent adverse events (TEAEs), serious TEAEs, and TEAEs causing premature discontinuation. An adverse event is treatment-emergent if it occurs or worsens after the first dose of randomized study treatment. Furthermore, frequencies will be given of subjects with TEAEs by system organ class, by system organ class and preferred term, by system organ class, preferred term and maximal severity, by system organ class, preferred term and strongest relationship, and by system organ class, preferred term, maximal severity, and strongest relationship. Separate analyses will be performed for ocular specific and all adverse events (including systemic).

Other safety endpoints including visual acuity, slit lamp biomicroscopy, intraocular pressure (IOP), tear osmolarity and dilated fundoscopy will be summarized by treatment group and visit using descriptive statistics. Changes or shifts from baseline will also be summarized where appropriate. For assessments performed by eye, worst eye (study eye) and fellow eye will be summarized separately.

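### Protocol 10.1 exempts dry eye exacerbation from AE reporting with no visible limit by seriousness, suspected causality or discontinuation, so such worsening may escape causality assessment and the TEAE tables

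*Protocol*

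**What the plan says.** Two sentences in Protocol Section 10.1 bear on the same events. The first is general: "Any clinically relevant deterioration in clinical finding is considered an AE and must be recorded". The second closes the section: "Exacerbation of conditions related to the signs and symptoms of Dry Eye will not be reported as an AE". The section does not say how they fit together, and attaches no condition to the second.

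The later safety sections build on the AE classification:

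- 10.1.2: "The Investigator must assess whether they consider an AE to be drug-related".
- 10.2: "An AE is considered serious if, in the view of either the investigator or Sponsor, it results in any of the following outcomes". A note there adds: "A serious adverse event (SAE) specifically related to visual threat would be interpreted as any potential impairment or damage to the" eyes of the subject, with central corneal ulcer among its examples.
- 10.3.1: AEs that are both suspected and unexpected "are to be reported to Ora, the Sponsor and the IRB/IEC as required by the IRB/IEC, federal, state, or local regulations".
- 10.3.2: "all SAEs, regardless of relationship to the IP, must be immediately reported".
- 11.4.9: "Frequencies and percentages will be provided per treatment group of subjects with treatment-emergent adverse events (TEAEs), serious TEAEs, and TEAEs causing premature discontinuation".

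SAP Section 15.1 repeats the general AE definition and plans a table of TEAEs that led to premature discontinuation. It contains neither the deterioration sentence nor the exemption.

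**The concern.** Exempting the disease under study from AE reporting is understandable: dry eye fluctuates, and its signs and symptoms are measured as efficacy outcomes against a concurrent vehicle arm. The difficulty is that the exemption is unbounded. Read as written, it covers ordinary fluctuation, but it also covers worsening that the investigator thinks the drops caused and worsening that makes a subject stop. It may cover serious worsening too.

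What could be lost is the individual judgement (was this related, was it serious, what was done) and the matching entry in the AE tables by arm. Evaluating safety is part of the stated objective in Section 3, and Section 5 already foresees subjects who terminate early and move to another dry eye therapy. The protocol does not say how often dry eye worsening would be the reason.

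**Working it through.** There is no figure to reproduce, and no arithmetic applies. The check sets the sections side by side and asks where an exempted event would go.

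**Step 1: can the two sentences of 10.1 be read together?** Yes. The last sentence can be taken as a specific exception to the general rule. That removes the direct contradiction, but leaves an exception with no limit.

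**Step 2: what starts each later safety step?**

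| Step | Section | Starts from | Mentions the exemption? |
|---|---|---|---|
| Causality assessment | Protocol 10.1.2 | an AE | no |
| Seriousness | Protocol 10.2 | an AE | no |
| Suspected unexpected reporting | Protocol 10.3.1 | an AE | no |
| Immediate SAE reporting | Protocol 10.3.2 | an SAE, hence an AE | no |
| TEAE tables | Protocol 11.4.9, SAP 15.1 | a recorded AE | no |

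**Step 3: follow the three kinds of worsening that matter.**

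- *Serious.* If 10.1 governs, the event is not an AE and so falls outside the SAE definition. If the visual-threat note and 10.3.2 govern, it is reported. The text supports either reading and sets no precedence.
- *Suspected to be related, not serious.* Nothing visible brings it back. Causality is assessed only for AEs, so the judgement that would flag the event need not be made.
- *Leading to discontinuation.* Section 9.6.2 puts the reason on the eCRF. The planned safety table counts TEAEs, so an exempted event need not appear in it.

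**Step 4: what remains visible without an AE record?**

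- Visual acuity and slit lamp, listed as safety measures in 7.2, are done at every scheduled visit (9.3.2 to 9.3.10) and summarised by arm, with changes or shifts from baseline where appropriate (11.4.9).
- The dryness endpoint (Protocol 7.1.2) and the nasal staining endpoints (SAP 13.2 and 13.3.1) would show average worsening by arm.
- Subjects who stop early should have the Visit 9 safety evaluations, on the day or at the investigator's discretion (9.3.11).
- Discontinuation reasons are on the eCRF (9.6.2), and disposition is summarised by treatment group (11.4.1).

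None of these records carries a causality or seriousness judgement.

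**Step 5: does the SAP settle it?** Not in the readable text. Its definition taken alone would include dry eye worsening, but its tables can summarise only what sites recorded, and sites follow the protocol.

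**The case against.** The strongest reply is that little is truly hidden. Dry eye worsening is the outcome being measured, acuity and slit lamp are checked at every visit and compared between arms, early leavers are examined, and disposition is summarised by arm. For serious cases the visual-threat note is broad, either the investigator or the sponsor can call an event serious, and all SAEs must be reported whatever their cause.

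Much of this stands, and it rules out stronger readings that a reader might infer:

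- *That the protocol bars reporting of serious eye damage.* It does not. The note in 10.2 and the duty in 10.3.2 could well lead a site to report it. What is missing is a statement of precedence.
- *That worsening would go unseen.* The records in Step 4 show otherwise.
- *That stinging after instillation would be exempted.* Section 2.1 names ocular discomfort and stinging as the most frequent AE in previous trials, so they were recorded as AEs there. Nothing in 10.1 says otherwise for this trial.
- *That the AE comparison would be biased in a known direction or by a known amount.* The documents give no basis for either.

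Two things survive. Summaries by arm do not replace an individual relatedness or seriousness judgement. And the reply offers no route into the AE record for non-serious worsening that is suspected to be drug-related or causes a subject to stop.

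A limit on the exemption could also sit in text that cannot be seen: parts of the protocol were removed and SAP Section 16 is redacted. Neither Protocol 10.1 nor SAP 15.1, both readable on this point, contains one.

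**Conclusion.** The concern holds as a gap in a stated rule. As written, the exemption allows suspected-related or discontinuation-causing dry eye worsening to bypass causality assessment, suspected-unexpected reporting and the TEAE tables. For serious worsening the protocol is ambiguous, with two rules and no order between them.

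No magnitude is stated, because neither the number nor the direction of affected events can be determined from the documents. The conclusion assumes that sites apply the last sentence of 10.1 literally and that no limit sits in the unseen text. It does not imply that the exemption itself is wrong: for ordinary fluctuation of the disease it is a reasonable choice.

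**What to change.** Reconcile the two sentences in Protocol 10.1 by adding one more. It should state that the exemption does not apply to dry eye worsening that meets a seriousness criterion in 10.2, is suspected to be related to the investigational product, or leads to discontinuation, and that such events are recorded as AEs and tabulated by arm. Put the same rule in SAP 15.1 so that the tables follow it. Leave the exemption in place for other dry eye fluctuation.

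The cost is small but not nil. Investigators must make a brief relatedness judgement on reported dry eye worsening before treating it as exempt, sites need a reminder, and some additional AE entries will follow. No new visit is needed, because AE queries are already listed at every scheduled visit.

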10.1.1 Severity

Severity of an AE is defined as a qualitative assessment of the degree of intensity of an AE as determined by the investigator or reported to him/her by the subject. The assessment of severity is made irrespective of relationship to IP or seriousness of the event and should be evaluated according to the following scale:

- [REDACTED]
- [REDACTED]
- [REDACTED]
- [REDACTED]
- [REDACTED]

10.1.2 Relationship to Investigational Product

The Investigator must assess whether they consider an AE to be drug-related. In assessing this relationship, the Investigator must use information about the conditions/concurrent medication, and chronology of the event relative to drug administration. The following definitions will be used:

- ***Definitely Related***
- ***Probably Related***
- ***Possibly Related***
- ***Unlikely to be related***
- ***Not Related***

10.1.3 Expectedness

The expectedness of an AE should be determined based upon existing safety information about the IP using these explanations:

- ***Unexpected:*** An AE that is not listed in the Investigator's Brochure (IB) or is not listed at the specificity or severity that has been observed.
- ***Expected:*** An AE that is listed in the IB at the specificity and severity that has been observed.
- ***Not applicable:*** An AE unrelated to the IP.

AE events that are mentioned in the IB as occurring with a class of products or as anticipated from the pharmacological/mechanical (or other) properties of the product, but are not specifically mentioned as occurring with the particular product under investigation are to be considered unexpected.

The investigator should initially classify the expectedness of an AE, but the final classification is subject to the Medical Monitor's determination.

10.2 Serious Adverse Events

An AE is considered serious if, in the view of either the investigator or Sponsor, it results in any of the following outcomes:

- Death;
- A life-threatening AE;

Note: An AE is considered "life-threatening" if, in the view of either the investigator or Sponsor, its occurrence places the subject at immediate risk of death. It does not include an AE that, had it occurred in a more severe form, might have caused death.

- Inpatient hospitalization or prolongation of existing hospitalization;

Note: The term "inpatient hospitalization" refers to any inpatient admission (even if less than 24 hours). For chronic or long-term inpatients, inpatient admission includes transfer within the hospital to an acute/intensive care inpatient unit. Inpatient hospitalization does not include: emergency room visits; outpatient/same-day/ambulatory procedures; observation/short stay units; rehabilitation facilities; hospice facilities; nursing homes; or clinical research/phase 1 units.

Note: The term “prolongation of existing hospitalization” refers to any extension of an inpatient hospitalization beyond the stay anticipated or required for the reason for the initial admission as determined by the investigator or treating physician.

- A persistent or significant incapacity or substantial disruption of the ability to conduct normal life functions;

Note: A serious adverse event (SAE) specifically related to visual threat would be interpreted as any potential impairment or damage to the subject’s eyes (e.g., hemorrhage, retinal detachment, central corneal ulcer or damage to the optic nerve).

- A congenital anomaly/birth defect.
- Important medical events that may not result in death, are life-threatening, or require hospitalization may be considered serious when, based upon appropriate medical judgment, they may jeopardize the subject and may require medical or surgical intervention to prevent one of the outcomes listed in this definition.

10.3 Procedures for Reporting Adverse Events

All AEs and their outcomes must be reported to Ora, the Sponsor, and the IRB/IEC as required by the IRB/IEC, federal, state, or local regulations and governing health authorities and recorded on the appropriate CRF. Adverse Events will be collected after the signing of the Informed Consent.

10.3.1 Reporting a Suspected Unexpected Adverse Reaction

All AEs that are ‘suspected’ and ‘unexpected’ are to be reported to Ora, the Sponsor and the IRB/IEC as required by the IRB/IEC, federal, state, or local regulations and governing health authorities.

10.3.2 Reporting a Serious Adverse Event

To ensure subject safety, all SAEs, regardless of relationship to the IP, must be immediately reported. All information relevant to the SAE must be recorded on the appropriate CRFs. The investigator is obligated to pursue and obtain information requested by Ora and/or the Sponsor in addition to that information reported on the CRF. All subjects experiencing a SAE must be followed up and the outcome reported.

In the event of a SAE, the investigator must notify Ora and the Sponsor immediately; obtain and maintain in his/her files all pertinent medical records, information, and medical judgments from colleagues who assisted in the treatment and follow-up of the subject; provide Ora and the Sponsor with a complete case history, which includes a statement as to whether the event was or was not suspected to be related to the use of the IP; and inform the IRB/IEC of the SAE within their guidelines for reporting SAEs.

Contact information for reporting SAEs:

[REDACTED]	[REDACTED]

